### 5.2. Statistical Analysis of Primary Measures

The primary efficacy endpoint for this study is CFB to 6 months post-treatment in 1-hr pad weight. Analysis of covariance (ANCOVA) with treatment group, study site and Baseline 1-hr pad weight as independent variables, will be used to analyze the primary efficacy endpoint. The FAS will be used, with subjects included in their randomized treatment group regardless of the treatment they actually received. The Baseline 1-hr pad weight is defined as the 1-hr pad weight at the Screening Visit. Missing values for the 6 month 1-hr pad weight will be imputed using a multiple imputation method that assumes the data are missing at random. Imputed datasets will be analyzed using an ANCOVA model with treatment group, study site, and Baseline 1-hr pad weight as independent variables. Approximately 100 imputed datasets will be created, with results from the analysis of each imputed dataset combined using Rubin's method. The adjusted mean change (AMC) and standard error (SE) will be provided for both treatment groups, along with the difference in AMC, its 95% confidence interval (CI) and associated p-value. The AMCs for each study site will also be provided.

Assuming the data is missing at random and the pattern of missing data is monotone the following generalized code will be used.

```
PROC MI data=Widedataset nopolish out=outmi seed=501213 NIMPUTE = 100;
class Treatment Site; /* */
monotone reg (CFB /details);
var Treatment Site V1PW CFB ;
run;

/* NOTE: Although currently shown below together in one model PROC MIXED may
need to be run twice once for the lsmeans and once for the differences, in order to
work well in MIANALYZE. */

PROC MIXED data=outmi;
class Treat Site;
model CFB = Treatment V1PW Site /solution covb;
lsmeans treat/ pdiff cl;
by _imputation_;
ods output solutionf=mxparms CovB=mxcovb lsmeans=lsmeans_ds(drop=effect)
diffs=pdiff ;
run;
```

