#### **4.2.6 Visit 4 (Month 3)**

The following procedures will be carried out at Visit 4 (Month 3):

- Concomitant therapy and medications assessment
- Adverse events assessment
- Vital signs assessment
- Collection and scoring of 3-day bladder voiding diary
- 1-hr pad weight test
- Subjects will be asked to fill out the following questionnaires:
  - UDI-6
  - ICIQ-UI-SF
  - I-QOL
  - FSFI
- Distribute and re-train subject on 3-day bladder voiding diary
- Request that the subject comes to Visit 5 with a full bladder

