### 10.5 EFFICACY ANALYSIS

#### 10.5.1 Primary Efficacy Endpoint Analysis

The primary efficacy endpoint for this study is CFB to 6 months post-treatment in 1-hr pad weight. Analysis of covariance (ANCOVA) with treatment group, study site and Baseline 1-hr pad weight as independent variables, will be used to analyze the primary efficacy endpoint. The FAS will be used, with subjects included in their randomized treatment group regardless of the treatment they actually received. The Baseline 1-hr pad weight is defined as the 1-hr pad weight at the Screening Visit. Missing values for the 6 month 1-hr pad weight will be imputed using a multiple imputation method that assumes the data are missing at random. Imputed datasets will be analyzed using an ANCOVA model with treatment group, study site, and Baseline 1-hr pad weight as independent variables.

Approximately 100 imputed datasets will be created, with results from the analysis of each imputed dataset combined using Rubin's method. The adjusted mean change and standard error (SE) will be provided for both treatment groups, along with the difference in adjusted mean change, its 95% confidence interval (CI) and associated p-value. The adjusted mean changes for each study site will also be provided.

A confirmatory analysis of the primary efficacy endpoint will be performed using the FAS and same ANCOVA as the primary analysis, but using only observed case data (no imputation will be performed for missing data). A second confirmatory analysis of the primary efficacy endpoint will be performed using the mITT, using only observed case data.

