##### 5.1.1.2 Modified Intent-to-Treat Population

The Modified ITT (mITT) includes all randomized subjects who are treated and complete the study. The mITT will be used for confirmatory analysis of efficacy endpoints.

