#### PROC MIANALYZE

SAS Usage Note 30715 (link provided in references) will be modified appropriately and used to transfer the data between PROC MIXED and PROC MIANALYZE for the lsmeans and their differences

Note1: To facilitate transfer of data between PROCs, the Treatment variable will contain only 1 word treatment descriptions: Viveve or Sham, likewise for Site, e.g. 201, 202

A confirmatory analysis of the primary efficacy endpoint will be performed using the FAS and same ANCOVA as the primary analysis, but using only observed case data (no imputation will be performed for missing data). A second confirmatory analysis of the primary efficacy endpoint will be performed using the mITT, using only observed case data.

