## **5.8. Handling of Dropouts and Missing Data**

Subjects who discontinue the study prior to completion will not be replaced. Imputation will be utilized for the primary endpoint analysis, the description of which is found in Section 5.2. No other imputation is planned. Missing data will be considered missing at random.

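### The primary multiple imputation uses only the ANCOVA covariates, so it repeats the observed-case analysis; the Month 3 pad weight is unused and no analysis departs from missing at random

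*SAP*

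**What the plan says.** Protocol 10.5.1 requires missing Month 6 values to be "imputed using a multiple imputation method that assumes the data are missing at random". It names no predictors. SAP 5.2 repeats this, adds that "Approximately 100 imputed datasets will be created", and gives SAS code with the only imputation model in either document. Its variable list is "var Treatment Site V1PW CFB": arm, site, baseline 1-hr pad weight and Month 6 change, with change imputed by monotone regression on the other three. The analysis step then models change on treatment, baseline and site. The SAP calls the code generalised and makes it conditional on a monotone pattern.

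Two confirmatory analyses follow in SAP 5.2, both on observed cases: the same ANCOVA on the FAS, and an analysis of the mITT, which "includes all randomized subjects who are treated and complete the study" (SAP 5.1.1.2). SAP 5.8 states: "No other imputation is planned. Missing data will be considered missing at random". SAP 5.10, on validity and robustness, only refers back to 5.2 and 5.3.

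Protocol 4.2.6 and Table 1 schedule the "1-hr pad weight test" at Month 3 as well, and SAP 4.1.4 lists the Month 3 change as an exploratory endpoint.

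**The concern.** An imputation helps when it brings in information that the analysis model lacks. Here the two models hold the same terms, so the imputation adds none. The plan appears to offer a primary result and two checks, but all three rest on nearly the same women with a Month 6 value and on the same assumption: that, given arm, site and baseline, missing Month 6 values resemble observed ones. Agreement among the three would say little about robustness to missing data.

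The obvious predictor is the same test three months earlier. If leaving after Visit 4 depends on the Month 3 result, the stated assumption fails and the estimated difference can be biased in either direction. None of the three analyses would reveal it.

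**Working it through.** **Step 1: the plan's own figures.** SAP 5.6 gives about 90% and 80% power for 66 vs 33, a difference of 20, and SD 28 or 33. The noncentrality is 20 / (SD × √(1/66 + 1/33)) = 20 / (SD × 0.2132), that is 3.35 and 2.84 on 97 df. Two-sided 5% power is 91.3% and 80.4%, so the figures reproduce. They take all 99 women as analysed; no dropout rate is stated anywhere.

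**Step 2: why the imputation repeats the observed-case ANCOVA.** Baseline is an eligibility measure and should be complete, so only the outcome is imputed. Let A = X'X over women with a Month 6 value, M = X'X over women without one, and b the observed-case ANCOVA estimate. Each imputation draws b* around b with variance σ²A⁻¹, fills in Xb* plus noise, and refits.
- Mean of the refitted estimate over draws: (A+M)⁻¹(Ab + Mb) = b.
- Within-imputation variance: σ²(A+M)⁻¹.
- Between-imputation variance: σ²(A+M)⁻¹(MA⁻¹M + M)(A+M)⁻¹ = σ²(A+M)⁻¹MA⁻¹.
- Sum: σ²(A+M)⁻¹(I + MA⁻¹) = σ²A⁻¹, the observed-case variance.

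This treats σ² as fixed and the number of imputations as large. It holds whatever the dropout rate or the Month 3 to Month 6 correlation.

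**Step 3: numerical confirmation.** The inputs below are assumptions, except the 66:33 split and the 100 imputations.
- Set A: 1000 trials per cell; true difference 20% × 27.5 g (midpoint of the 5 to 50 g window) = 5.5 g at Months 3 and 6; residual SD 8.5 g; uniform baseline with slope -0.3; 8 sites with SD 1 g. Correlation of planned imputation with observed-case ANCOVA 0.9989 to 0.9998; mean absolute gap 0.03 to 0.08 g; SE 1.91 to 2.10 g against 1.91 to 2.08 g.
- Set B: 300 trials in each of 18 scenarios; true difference 5 g; residual SD 12 g; 9 sites; 5% to 20% missing. Mean estimates agree within 0.01 g; correlation at least 0.9988; imputation SE 0.1% to 0.9% larger. With 3000 imputations (20% missing) the mean gap per trial falls to 0.016 g, so it is simulation noise.

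**Step 4: bias of the planned imputation when dropout depends on Month 3 (Set A).** The dropout log-odds rise 1.2 per SD of poorer Month 3 response. Bias is measured against the full-data ANCOVA of the same trial (Monte Carlo SE 0.01 to 0.03 g). Positive values overstate the device's benefit. Percentages are dropout in the affected arm(s); r is the Month 3 to Month 6 correlation.

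| Who leaves | 10%, r 0.5 | 15%, r 0.6 | 17%, r 0.7 |
|---|---|---|---|
| Active arm only | +0.46 g | +0.76 g | +1.00 g |
| Sham arm only | -0.44 g | -0.81 g | -1.00 g |
| Both arms, one rule on actual Month 3 change | -0.17 g | -0.33 g | -0.45 g |
| Both arms, one rule on Month 3 residual | -0.01 g | +0.01 g | +0.01 g |

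The third row is negative because, if the device works, more sham women respond poorly and leave, which flatters sham. With Month 3 change in the imputation, bias is at most 0.03 g in all 12 cells.

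**Step 5: limits of adding Month 3.** If half the dropouts leave before Visit 4 (15%, r 0.6), the first three rules leave +0.36, -0.37 and -0.13 g, against +0.77, -0.79 and -0.32 g as planned in that run: roughly half. If dropout in the active arm depends on the Month 6 value itself (Set B, 10% missing overall, r 0.8), full data give -5.12 g, the planned imputation -7.25 g and the imputation with Month 3 -5.96 g. The bias falls from 2.13 to 0.84 g but does not vanish.

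**Step 6: sensitivity to inputs.** Set B uses a steeper rule: active-arm log-odds rise 2 per SD of poorer Month 3 response, with random dropout in sham. At 10% missing overall and r 0.8 the planned imputation gives -6.56 g, full data -4.81 g and the imputation with Month 3 -4.78 g: a bias of 1.75 g, removed. At 20% the first two are -8.17 and -5.16 g, a bias of about 3.0 g against an SE of 2.7 g.

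**The case against.** The plan does not contradict itself. The protocol asks for multiple imputation under missing at random, and the SAP supplies it. The code is described as generalised, its variable names are not consistent (Treat and Treatment), and the prose bars no predictor. That stands: this is a better method, not a breach. But no other model is stated, and nothing commits the sponsor to using Month 3.

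The larger biases need a rule that differs by arm, and the trial is double-blind with tips that look and behave alike (Protocol 8.1). The documents give no reason to expect such a rule, though they do not exclude it. With no true effect (2000 trials per cell, observed-case ANCOVA as stand-in), a common rule gave bias of at most 0.03 g and rejection rates of 4.4% to 5.8%; the active-only rule gave 6.2% to 7.9%. So a common rule does not inflate false positives in these runs.

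The gram figures are illustrative. Dropout and correlation rise together in the table. At 5% dropout the active-only bias is +0.23 to +0.33 g, about one-eighth to one-sixth of the SE. The simulation lets pad weights go below zero; flooring them lowers the 15% active-only figure from 0.75 to 0.68 g. All this limits what can be said about size. None of it touches Step 2.

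The separate Month 3 analysis (SAP 5.3) and the recorded withdrawal reasons (Protocol 5.3) would help a reader notice Month 3-related dropout, but they correct nothing.

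**Conclusion.** The concern holds. As stated, the primary imputation is the observed-case ANCOVA with simulation noise added. That follows from the model and does not depend on assumed inputs, provided baseline is complete. The confirmatory analyses therefore give almost no information on missing data, and no analysis departs from missing at random.

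The size of any bias cannot be known from the documents, and neither can its sign. Under the moderate assumptions it runs from -1.00 to +1.00 g, at most about half of a 2 g SE, and is near zero under one plausible rule. Under harsher assumptions it can exceed one SE, so half an SE is not a bound. The primary analysis is not invalid, but its key assumption is untested and its best predictor is unused. The change should be made.

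**What to change.** 1. Put Month 3 change before Month 6 change in the imputation: `var Treatment Site <Screening 1-hr pad weight> CFB_M3 CFB_M6; monotone reg(CFB_M3 CFB_M6);`. Leave the ANCOVA unchanged.
2. Name the method (FCS, for example) for women who miss Month 3 but have Month 6, since that pattern is not monotone.
3. Keep both observed-case analyses.
4. Add one supporting analysis that departs from missing at random, and choose it now: either a delta-adjusted imputation that raises active-arm missing values in 1 g steps until the conclusion changes, or a sham-based imputation. An active-arm shift tests only one direction, so if it is chosen, also shift sham values, and say what is reported if the primary result is not significant.
5. Report by arm how many women with missing Month 6 data have a Month 3 value, because item 1 cannot help the others.
6. State the imputation scale if the non-normality fallback in SAP 5.3 is used.

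The cost is a few lines of SAP code and one table, fixed before unblinding at final database lock. The Month 3 test is already scheduled, the protocol's imputation wording allows the change, and no protocol-specified analysis is removed.

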#### PROC MIANALYZE

SAS Usage Note 30715 (link provided in references) will be modified appropriately and used to transfer the data between PROC MIXED and PROC MIANALYZE for the lsmeans and their differences

Note1: To facilitate transfer of data between PROCs, the Treatment variable will contain only 1 word treatment descriptions: Viveve or Sham, likewise for Site, e.g. 201, 202

A confirmatory analysis of the primary efficacy endpoint will be performed using the FAS and same ANCOVA as the primary analysis, but using only observed case data (no imputation will be performed for missing data). A second confirmatory analysis of the primary efficacy endpoint will be performed using the mITT, using only observed case data.

### 5.3. Exploratory Efficacy Endpoint Analyses

Exploratory efficacy endpoints include CFB to 3 months post-treatment in 1-hr pad weight; CFB to 6 months post-treatment in 24-hr pad weight; CFB to 3 and 6 months post-treatment in 3-day bladder voiding diary; CFB to 3 and 6 months post-treatment in UDI-6, ICIQ-UI-SF and I-QOL; and CFB to 3 and 6 months post-treatment in FSFI total score, in subjects with FSFI total score  $\leq 26.5$  at Baseline. For the exploratory efficacy endpoints a significance level of 0.05 will be used; given the large number of endpoints, the p values for those endpoints will be considered descriptive.

Scoring of the UDI-6, ICIQ-UI-SF, I-QOL, and FSFI questionnaires is described in the separate Questionnaire Completion and Scoring Guideline document. Included in that document are rules for obtaining the total score for each questionnaire. The impact of missing items on the total score is discussed. If the total score cannot be computed based on the rules provided, e.g. there are too many items with no response, no further

imputation will be implemented. This lack of imputation matches the handling of other exploratory endpoints discussed in the paragraph below.

Each of the continuous endpoints will be analyzed using ANCOVA with treatment group, study site, and the relevant Baseline as independent factors. The FAS population will be used for each analysis (for the FSFI analyses, the FAS subjects with a Baseline FSFI total score  $\leq 26.5$  will be used), with subjects included in their randomized treatment group regardless of the treatment they actually received. Baseline for each endpoint is the relevant value from the Screening Visit. For each of the exploratory endpoints, only observed case data will be used (no imputation will be performed for missing data). Output from each ANCOVA will include the AMC and SE for the active treatment and sham groups, as well as the difference in AMC, its 95% CI, and p-value. The AMCs for each study site will also be provided for each ANCOVA.

Confirmatory analyses will be performed for each of the exploratory endpoints, using the mITT with observed case data only (no imputation for missing data will be performed).

For all continuous endpoints (primary and exploratory), the assumption of normality will be assessed. If any endpoint at any time point is found to be not normally distributed, the data will either be transformed to make it normal or a nonparametric test will be used instead of the planned ANCOVA.

The analyses described above for the primary and exploratory efficacy endpoints will be carried out using SAS (Version 9.4 or above) Proc Mixed, Proc MI, and Proc MIANALYZE as appropriate (Yuan 2000, 2011, [SAS Usage Note 30715](#)).

#### **5.4. Statistical Analyses of Safety Measures**

No statistical analyses will be performed on any of the safety data in this study. The SP will be used for all safety summarizations, with subjects included in the treatment group they actually received regardless of their randomized treatment group. AEs will be coded using definitions in the most recent version of Medical Dictionary for Regulatory Activities (MedDRA; Version 22.0.) Each AE will be coded with its appropriate Preferred Term (PT), and linked with its associated System Organ Class (SOC). AEs will be summarized using treatment-emergent AEs (TEAEs, defined as AEs that begin or worsen after the Viveve procedure [sham or active] is initiated). TEAEs and serious AEs (SAEs) will be summarized by SOC, severity, and relationship to study treatment for each treatment group. All AEs (TEAE and non-TEAE) will be provided in a listing. For screen failed subjects only AEs classified as SAEs will be reported.

No descriptive statistics are planned for vital signs or safety laboratory measurements, but data will be available in a listing.

#### **5.5. Mid-study Analysis**

A prospective analysis was to be performed after ~80 subjects have completed their 3-month visit. However, prior to this time, the sponsor decided not to perform the Mid-Study Analysis in order to maintain the LIBERATE International study integrity. The Mid-Study Analysis could potentially impact study data integrity.

When the last subject has completed her 6-month visit, the final database lock will occur for all data for all subjects. At this time, the database will be fully unblinded and all protocol-defined analyses and summaries will occur.

## **5.6. Sample Size Justification**

The primary efficacy endpoint for this study is CFB to 6 months post-treatment in the 1-hr pad weight. A clinically meaningful reduction in the 1-hr pad weight is >50% (target reduction in the active treatment group); a sham (placebo) effect of a 30% reduction is anticipated in the sham group. The sample size for this study will be ~99 randomized subjects, in a 2:1 ratio with ~66 randomized to the active treatment group and ~33 to the sham treatment group. Assumptions include a 2-sided t-test at the 5% level of significance, and a CFB to 6 months post-treatment of >50% in the active group and of 30% in the sham group. Thus, 99 total randomized subjects, in a 2:1 ratio to active:sham treatment groups, will provide approximately 90% power if the common standard deviation in CFB is as large as 28, and will provide approximately 80% power if the common standard deviation in CFB is as large as 33. Additionally, for the CFB to 6 months post-treatment in 1-hr pad weight, a sample size of 99 total randomized subjects, in a 2:1 ratio to active:sham treatment groups, will provide approximately 90% power if the effect size (difference in treatment means divided by the standard deviation) is as small as 0.698 and approximately 80% power if the effect size is as small as 0.603. Note that an effect size of 0.698 would be achieved if the difference between active and sham groups, in CFB to 6 months post-treatment, was 25 g and the standard deviation was 35.8; and an effect size of 0.603 would be achieved if the difference was 25 g and the standard deviation was 41.4.

## **5.7. Experiment Design and Randomization**

### **5.7.1. Experimental Design**

This is a randomized, double-blind, sham-controlled clinical study. The study is designed to demonstrate that active treatment (the Viveve Treatment, SUI protocol) is superior to the sham treatment for the efficacy endpoint, 1-hr pad weight test, and is deemed to have appropriate safety as compared to sham. Approximately ninety-nine (99) subjects meeting the inclusion and exclusion criteria will be randomized on Study Day 1 in a 2:1 ratio to either the active or sham treatment group. Randomization will be stratified by study site, with a maximum of 30 subjects randomized at an individual site. The active treatment group will receive a treatment dose of 90 J/cm^2 and the sham group will receive a sub-therapeutic dose of ≤1 J/cm^2.

Subjects will be followed out to a 6-month post-treatment visit.

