## **4 INVESTIGATIONAL PLAN**

### **4.1 STUDY DESIGN**

This is a randomized, double-blind, sham-controlled clinical trial. This study is designed to demonstrate that the active treatment (i.e., Viveve Treatment, SUI protocol) is superior to the sham treatment for the primary efficacy endpoint, 1-hr pad weight test. Approximately 99 subjects who meet the entry criteria will be randomized 2:1 to either the active or sham treatment group. Randomization will be stratified by study site, with a maximum of 21 subjects randomized at an individual site. The active group will receive a therapeutic dose of 90 J/cm^2 of RF energy and the sham group will receive a sub-treatment dose of ≤1 J/cm^2. Subjects will be followed out to a 6-month post-treatment visit.

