#### **3.2. Secondary Objectives**

The secondary objective of this study includes the determination of:

- Safety of the Viveve treatment from the treatment procedure through 6 months post-treatment.

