#### 4.1.2. Secondary Endpoints

#### 4.1.3. Safety Endpoints

Safety endpoints for this trial include:

- Safety as assessed by adverse event (AE) reporting from the treatment procedure to study completion for each subject.

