##### 5.1.1.3 Safety Population

The Safety Population (SP) includes all randomized subjects in whom the treatment procedure is started, regardless of if the procedure is completed. The SP will be used for all of the safety summaries.

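### The synopsis and SAP 5.7.1 state a comparative safety aim against sham, but no criterion is given and the planned analysis contains no between-arm estimate or interval

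*SAP*

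**What the plan says.** **The aim.** The synopsis (Overview of Study Design) and SAP 5.7.1 attach a second clause to the efficacy superiority aim, namely that active treatment "is deemed to have appropriate safety as compared to sham". Neither place says what would count as appropriate, which events matter, or who decides.

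**The analysis.** SAP 5.4 states: "No statistical analyses will be performed on any of the safety data in this study". Protocol 10.6 and the Safety Evaluation part of the synopsis carry the same sentence. What is planned is descriptive: "TEAEs and serious AEs (SAEs) will be summarized by SOC, severity, and relationship to study treatment for each treatment group". Protocol 10.6 adds deaths and withdrawals due to adverse events by group. For the remaining safety data, SAP 5.4 says: "No descriptive statistics are planned for vital signs or safety laboratory measurements, but data will be available in a listing". The Safety Population "includes all randomized subjects in whom the treatment procedure is started, regardless of if the procedure is completed", analysed by treatment received.

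**The rest of the plan.** Protocol 4.1 limits the design aim to showing that active treatment "is superior to the sham treatment for the primary efficacy endpoint, 1-hr pad weight test". The secondary objective is worded without a comparator: "Safety of the Viveve treatment from the treatment procedure through 6 months post-treatment" (SAP 3.2; similarly Protocol 3.3). So is the endpoint: "Safety as assessed by adverse event (AE) reporting from the treatment procedure to study completion for each subject" (SAP 4.1.3; similarly Protocol 3.3.1). The sample size sections (Protocol 10.1, SAP 5.6) rest on pad weight alone.

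**The concern.** A statement about safety relative to sham needs a contrast between the arms and some indication of its precision. The plan names such a statement as something the study is designed to show, and then excludes the analysis that would supply either. With no criterion fixed in advance, any judgement of appropriateness would be made after unblinding, with the counts in view.

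What is at stake is how the safety result is read. Similar or zero counts in two columns look reassuring. At these arm sizes they can be compatible with a sizeable excess on active treatment, and a table of counts and percentages does not show that. The efficacy result is not touched.

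**Working it through.** **1. The plan's own figure.** The only power stated is for pad weight. Inputs (SAP 5.6): 66 versus 33, two-sided 5% t-test, 50% versus 30% reduction (difference 20), SD 28 or 33. The noncentrality parameter is (difference/SD) × √(66×33/99) = (difference/SD) × √22. From the noncentral t distribution with 97 degrees of freedom:

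| Input | Power stated | Power recomputed |
|---|---|---|
| SD 28 | about 90% | 91.3% |
| SD 33 | about 80% | 80.4% |
| Effect size 0.698 | about 90% | 90.0% |
| Effect size 0.603 | about 80% | 80.0% |

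These reproduce. No safety rate, margin, precision or power is given anywhere, so there is no safety figure to reproduce.

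**2. Precision of a comparison with sham.** Arm sizes are the planned ~66 and ~33, assuming that nearly all randomized women start the procedure and receive their allocated treatment. **The event counts are assumptions**, since the documents give no adverse event rates. The Newcombe interval for d = p₁ − p₂ uses the Wilson limits (l, u) of each arm:

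- lower = d − √[(p₁ − l₁)² + (u₂ − p₂)²]
- upper = d + √[(u₁ − p₁)² + (p₂ − l₂)²]

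| Active | Sham | Wilson limits, active | Wilson limits, sham | d (points) | 95% CI (points) |
|---|---|---|---|---|---|
| 0/66 | 0/33 | 0 to 5.5% | 0 to 10.4% | 0.0 | -10.4 to +5.5 |
| 7/66 (10.6%) | 3/33 (9.1%) | 5.2 to 20.3% | 3.1 to 23.6% | +1.5 | -13.9 to +12.9 |
| 13/66 (19.7%) | 5/33 (15.2%) | 11.9 to 30.8% | 6.7 to 30.9% | +4.5 | -13.1 to +18.6 |

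For the active arm alone, 0/66 has an exact one-sided 95% upper limit of 1 − 0.05^(1/66) = 4.4%.

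**3. The same over a range of rates.** With equal true rates p in both arms, the approximate half-width is 1.96 × √[p(1 − p)(1/66 + 1/33)]. This gives ±9.1, ±12.5, ±16.7, ±19.1 and ±20.9 points for p = 5%, 10%, 20%, 30% and 50%. Power to detect a rise from 10% on sham to 20% on active is about 22% (normal approximation) or 19% (Fisher's exact test).

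**4. Dependence on a margin.** Power to exclude an excess of size m when the true rates are equal is Φ(m/SE − 1.96), with SE = √[p(1 − p)(1/66 + 1/33)]. At p = 10%, SE = 0.0640:

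- m = 10 points: Φ(1.56 − 1.96) = 35%
- m = 20 points: Φ(3.13 − 1.96) = 88%

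For m = 10 points, power falls to 22% at p = 20% and 17% at p = 30%. Whether these numbers could support a comparative statement therefore depends on a margin that the plan does not state.

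**The case against.** The strongest reply is that the clause uses the language of judgement. It does not claim non-inferiority or equivalence, and saying that safety is deemed appropriate may mean no more than a clinical reading of the by-arm tables. Those tables are planned, and relatedness is assessed by both the investigator and the medical monitor (Protocol 4.2.8.1 and 9.1.3). Descriptive safety reporting is normal at this size. The comparative clause stands in only two places, while Protocol 4.1, the objective and the endpoint do not carry it. Intervals could also be calculated later from the reported counts.

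Most of this stands. A clinical judgement remains possible, and purely descriptive safety analysis is not itself a fault. What remains is the mismatch: a judgement relative to sham is announced as a design aim, with neither a criterion nor a between-arm estimate behind it. That intervals can be derived afterwards is a reason to plan them, since they cost almost nothing.

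A reader might infer that 66 versus 33 women cannot support any comparative safety conclusion. The documents do not establish that: it depends on the margin, and with a 20-point margin and a 10% event rate power would be 88%. A reader might also infer that the sponsor will present similar or zero counts as proof of safety equal to sham. No passage says so.

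Once the aim is reworded, the table of risk differences is no longer needed to remove the contradiction. It is a cheap improvement that makes the imprecision visible.

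**Conclusion.** The point holds as an inconsistency between a stated aim and the planned analysis, together with an inexpensive gap in reporting. The comparative safety clause in the synopsis and SAP 5.7.1 has no criterion and no between-arm analysis, and is out of line with Protocol 4.1 and with the safety objective and endpoint.

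As to size, a 95% interval for an adverse event risk difference would extend roughly 9 to 21 points either side of the estimate for event rates of 5% to 50%. Nearly equal counts such as 7/66 and 3/33 would leave an excess of up to about 13 points within the interval. These figures rest on assumed counts and rates and on arm sizes close to plan. They show imprecision and do not predict the trial's safety findings. The primary analysis, its error rate, the sample size and trial conduct are unaffected.

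**What to change.** 1. In the synopsis (Overview of Study Design) and SAP 5.7.1, replace the comparative safety clause with *and to describe safety in each arm*, in line with Protocol 4.1.
2. In all three places that exclude statistical analyses of safety (synopsis Safety Evaluation, Protocol 10.6, SAP 5.4), change the exclusion to *No hypothesis tests*. Changing only some of them would create a new contradiction.
3. In Protocol 10.6 and SAP 5.4, add a descriptive table in the Safety Population: the active-minus-sham risk difference with a 95% confidence interval (for example Newcombe) for any TEAE, any related or possibly related TEAE, and any SAE.

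The cost is a few wording changes and one short table. No new data are needed. The downside for the sponsor is that wide intervals will make the safety statement look less favourable than counts alone. No safety threshold is proposed here: if the comparative aim is to be kept, its criterion is for the sponsor to define before unblinding.
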